## PROTOCOL

### Effectiveness of Debriefing After a Short Training on Brief Tobacco Intervention for Nursing Students: A Randomized Clinical Trial

#### **Aim:**

The aim of this study was to determine the effectiveness of debriefing after objective evaluation of a brief tobacco intervention (BTI) training in nursing students, and its progression at 3 and 9 months.

#### **Method:**

##### Design

A randomized controlled clinical trial with block randomization was used to evaluate the debriefing intervention versus no debriefing, with five measurements taken over 9 months.

##### Sample and Setting

The study was conducted with second-year nursing students at the University of Murcia, Spain, during the 2021-2023 academic years. Inclusion criteria were being enrolled in the second-year course "Bases de Enfermería Comunitaria," where BTI training is provided, and agreeing to participate in the study. In the two academic years during which the research was conducted, 300 students were enrolled. The sample size was calculated using Pass 11 (Power Analysis & Sample Size) software for repeated measures ANOVA. For a repeated measures design with 1 between-factor and 1 within-factor, with 2 groups and 65 subjects each (total 130 subjects), each subject was measured 5 times. This design achieves 100% power to test the AB interaction if a Geisser-Greenhouse Corrected F Test is used with a 5% significance level and the actual effect standard deviation is 1.

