##### Developmental Process

Of the 300 eligible students, 145 agreed to participate. Block randomization was used for the random assignment of students to the experimental group (EG) and control group (CG). The unit of randomization was small groups (13-16 students/group), with all enrolled students assigned accordingly. Block randomization was performed using a random number generator, assigning 5 blocks to the experimental group (80 students) and 5 blocks to the control group (65 students).

Both groups (EG and CG) received BTI training in a brief format of 2.5 hours in groups of 13-16 students. The content included 1) general information and epidemiology of smoking, 2) passive smoking, 3) evidence of the effectiveness of smoking cessation interventions, and 4) the WHO's approach to smoking in Primary Care based on the 5 As and 5 Rs model to help patients quit smoking (World Health Organization, 2014). This model outlines the five main steps of the 5 As (Ask, Advise, Assess, Assist, and Arrange) for providing brief interventions in primary care and the 5 Rs (Relevance, Risks, Rewards, Roadblocks, and Repetition) to be addressed for a smoker who is not ready to quit at that moment.

The methodology included a phase of evaluating the students' learning using the Videotape Objective Structured Clinical Examination (VOSCE). Students were shown 3 recorded clinical scenarios (video-problems) with standardized patients in which a nursing professional performs a brief tobacco intervention (BTI) on a patient visiting a primary care clinic, following the 5 As and 5 Rs model. The videos depicted common errors in this type of intervention, and students were required to detect them using the validated BTI-St® assessment tool. The scenarios included the patient was not ready to quit smoking (scenarios 1 and 2) and was ready to quit (scenario 3).

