The data collection protocol was similar in both the EG and CG, with five measurements conducted each time after viewing the 3 video-problems and assessing learning through the BTI-St®. At baseline, before BTI training (T0); followed by training in BTI in Primary Care (T1). Subsequently, in the experimental group, an expert instructor conducted a structured debriefing lasting 10-15 minutes for each clinical scenario, whereas no further intervention was provided in the control group. At the end of the first day, all participants viewed the videos and completed the tool again (T2). At three and nine months, students viewed the videos and measurements were taken at T3 and T4, respectively.

The debriefing used had the following characteristics: short ( $\leq 15$  minutes), educator present, educator with debriefing experience, the context was related to health management or decision-making, and the method used was the plus-delta tool, which asks participants to reflect on the simulation event and evaluate their performance by identifying strengths and areas for improvement.

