## Method of Measurement

To assess the change in learning regarding brief tobacco cessation counseling among nursing students, the Brief Tobacco Intervention BTI-St© tool was used, incorporating the standardized patient videos described earlier. This instrument is based on a criterion-referenced or competency test model, enabling an objective evaluation of students' BTI performance and identifying learning deficiencies. It is presented as an algorithm consisting of 23 dichotomous items organized according to the 5As and 5Rs model and has demonstrated adequate validity and reliability (Ramos-Morcillo et al., 2022). Students must view a recorded clinical scenario and determine whether the brief intervention criteria for smoking cessation are met. Responses are corrected according to the gold standard defined during the scenario validation, with item scores ranging from 0 (incorrect) to 1 (correct). The maximum total score for each scenario ranges from 0 to 1 point if the student answers all items correctly.

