## Data Analysis

Descriptive analyses were conducted, calculating the mean and standard deviation for quantitative variables, and frequencies and percentages for qualitative variables. To compare the variables studied between the control and experimental groups, the t-Student test and Chi-Square test were used depending on the nature of the comparison variable.

The overall score of each student was calculated for each of the three cases and weighted according to the number of items they had to answer. Thus, the score in each case could range between 0 and 1. A two-factor repeated measures ANOVA was used to analyze the differences in within-subject and between-subject measures. The assumptions of this test include the condition of sphericity; if this assumption was violated, the multivariate approach, which does not require the variance-covariance matrix to be spherical, or the F statistic with modified degrees of freedom using the  $\epsilon$  correction factor (Greenhouse-Geisser estimate), was applied (Pardo Merino & San Martín Castellanos, 2011). A significance level of 5% ( $p \leq 0.05$ ) was utilized in the statistical analysis. Data analysis was performed using SPSS® v. 25 (Statistical Package for the Social Sciences).

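### The only power figure, 100%, is tied to an effect SD of 1 with no unit or error SD, so it cannot be read as power for a stated difference on the 0-1 score

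*Combined protocol and SAP*

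**What the plan says.** The sample size comes from a PASS 11 calculation for repeated measures ANOVA (Sample and Setting). The design is one between-subject and one within-subject factor, "with 2 groups and 65 subjects each (total 130 subjects"), with five measurements each. The claim is: "This design achieves 100% power to test the AB interaction", using a Geisser-Greenhouse corrected F test "with a 5% significance level and the actual effect standard deviation is 1". No unit, error SD, correlation, epsilon, pattern of means or target difference is given there, and no other section gives them or a second power figure.

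The outcome is on a unit scale. Method of Measurement says: "The maximum total score for each scenario ranges from 0 to 1 point if the student answers all items correctly". Data Analysis repeats it for the analysed score: "Thus, the score in each case could range between 0 and 1". The planned analysis is at student level: "A two-factor repeated measures ANOVA was used to analyze the differences in within-subject and between-subject measures".

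Two features of the design matter here. The arms are treated alike until after T1 (Developmental Process): "Subsequently, in the experimental group, an expert instructor conducted a structured debriefing lasting 10-15 minutes for each clinical scenario". Allocation was by group: "The unit of randomization was small groups (13-16 students/group"), five groups to each arm, giving 80 and 65 students.

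**The concern.** A power figure means something only when tied to a difference in the outcome being analysed. Here it is tied to a value of 1 in an unstated unit, while the outcome itself runs only from 0 to 1. The value looks like a figure entered without reference to the score.

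What is at stake is how the results are read, above all the progression at 3 and 9 months named in the Aim. If little difference is found at T3 or T4, a reader who trusts 100% power would conclude that no worthwhile effect exists. The documents do not allow that conclusion, because they do not show which score difference the trial could have detected.

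**Working it through.** **Inputs from the documents.** 2 arms, 5 times, 65 per arm, alpha 5%, effect SD 1 (Sample and Setting); score 0 to 1 (Method of Measurement, Data Analysis); arms differ only after T1, and 80 and 65 students in 5+5 groups, so on average 80/5 = 16 and 65/5 = 13 per group (Developmental Process).

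**Inputs assumed, because none is given.** Error SD σ, within-student correlation ρ, sphericity factor ε and intraclass correlation ICC. No dropout throughout.

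**1. The stated 100%.** For the interaction, λ = n·a·b·σ_AB² / [σ²(1−ρ)], with 4ε and 512ε degrees of freedom (4 × 128 = 512) and noncentrality ελ. The stated inputs do not fix λ.
- If σ = 1 and ρ = 0, λ = 65 × 2 × 5 × 1 = 650. Power is 100% for every ρ from 0 to 0.7 and ε from 0.25 to 1.
- If σ = 5 and ρ = 0, power is 99% (ε = 1) or 72% (ε = 0.25).
- If σ = 10 and ρ = 0, λ = 6.5 and power is 50% or 24%.

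So 100% can be reproduced only by supplying an error SD that the plan does not state.

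**2. Effect SD 1 in score points.** Let d_j be the arm difference at time j. The interaction SD is σ_AB = ½·SD(d_j) over the five times.
- Sustained gap (0, 0, D, D, D): mean 0.6D; sum of squares 2(0.36) + 3(0.16) = 1.20 D²; SD = √0.24·D = 0.490D; σ_AB = 0.245D. Then σ_AB = 1 needs D = 1/0.245 = 4.08 points.
- Ceiling for any pattern with d_j between −1 and 1: three at +1 and two at −1 give √(1 − 0.04) = 0.980, so σ_AB = 0.490.
- Ceiling for a same-sign effect at T2-T4 only: 0.245.
- If effect SD means the SD of the arm gaps, without halving, the overall ceiling is 0.98 and a sustained gap would have to be 1/0.490 = 2.04 points.

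The value 1 is out of reach under both definitions. This step assumes no score SD.

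**3. Effect SD 1 in SD units (σ = 1, an assumption).** The sustained gap is 4.08 SD, which fits a 0-1 score only if the score SD is at most 1/4.08 = 0.245. With 10 students per arm, λ = 10 × 2 × 5 = 100, and power is 99.7% even at ρ = 0 and ε = 0.25. Under the other definition the gap is 2.04 SD and λ = 25 with 10 per arm: 98% at ρ = 0 under sphericity, but 66% at ε = 0.25.

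**4. What the design might detect (illustration only).** In general λ = Σ(d_j − d̄)² / [σ²(1−ρ)(1/n_E + 1/n_C)].

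For a sustained 0.05-point gap with 65+65 independent students and sphericity, Σ = 1.2 × 0.0025 = 0.003 and 2/65 = 0.0308.
- Score SD 0.20, ρ = 0: λ = 0.003/(0.04 × 0.0308) = 2.44; power 20%.
- Score SD 0.15, ρ = 0.8: λ = 0.003/(0.0225 × 0.2 × 0.0308) = 21.7; power 97%.

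For 80+65, 1/80 + 1/65 = 0.0279. The student-level test (4 and 572 df) needs λ = 12.03 for 80% power, so at ρ = 0 the sustained gap is √(12.03 × 0.0279/1.2) = 0.53 SD. A test on the 10 group means (4 and 32 df) needs λ = 13.83. If group effects vary over time with ICC 0.05, the variance term becomes (1 + 15 × 0.05)/80 + (1 + 12 × 0.05)/65 = 0.0465, giving √(13.83 × 0.0465/1.2) = 0.73 SD. For the fading pattern (0, 0, D, D/2, D/4), Σ = 0.70 D² and D is the gap at T2.

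Smallest interaction gap with 80% power, 80+65, sphericity, in SD:

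| Analysis and pattern | ρ = 0 | ρ = 0.5 | ρ = 0.8 |
|---|---|---|---|
| Student level, sustained | 0.53 | 0.37 | 0.24 |
| Student level, fading | 0.69 | 0.49 | 0.31 |
| 10 group means, constant group effects, sustained | 0.57 | 0.40 | 0.25 |
| 10 group means, time-varying, ICC 0.05, sustained | 0.73 | 0.52 | 0.33 |

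In points, the first row is 0.08, 0.06, 0.04 at score SD 0.15 and 0.11, 0.07, 0.05 at SD 0.20. The last row is 0.11, 0.08, 0.05 and 0.15, 0.10, 0.07.

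A single unadjusted difference at T2, T3 or T4, tested at 5%, needs 0.47 SD without clustering (143 df). On group means (8 df) it needs 0.60, 0.69 or 0.82 SD at ICC 0.02, 0.05 or 0.10.

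**The case against.** The strongest reply is that the unit may be neither score points nor SDs. The instrument has 23 items scored 0 or 1. As a raw item count, a sustained gap of 4.08 items is 4.08/23 = 0.18 of the scale, which is not absurd. With an error SD of about 3.5 items (0.15 × 23), ρ = 0 and sphericity, 65+65 would have over 99% power, close to the stated figure, though 95% at ε = 0.25. This reading cannot be strictly excluded. It has no support in the text, since Data Analysis works with the 0-1 score. What stands is that one should not say the 100% describes no realistic difference. The defensible statement is that it cannot be interpreted as written.

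A second reply is that nothing is shown to be miscalculated. That also stands: 100% follows if the error SD is 1, so this is a missing-input and scale problem and not a proven software or arithmetic error. A reader might likewise infer from step 3 that 65 per arm was unjustified. That needs both an error SD of 1 and a particular definition of effect SD, and the plan states neither.

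Third, every input in step 4 is assumed, and ρ = 0 is a harsh lower end for repeated scores from the same students. True, so those figures are illustrative and not bounds. The impossibility in step 2 does not depend on them.

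Fourth, the loss from group randomisation is uncertain for the interaction. Group effects that stay constant over time cancel and cost only degrees of freedom. The documents do not say whether they are constant.

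**Conclusion.** The point holds as a reporting defect that should be corrected. The plan's only power figure cannot be interpreted as power for a stated score difference. Read on the analysed 0-1 scale, the effect behind it cannot occur (ceiling 0.49, or 0.245 for a same-sign effect at T2-T4, against a stated 1), and this rests only on the scale and the timing of debriefing. Read in SD units, it is a sustained gap of about 4 SD, or about 2 SD without halving, and that rests on an assumed error SD of 1. The figure also assumes 65+65 independent students, whereas 80+65 students in 5+5 randomised groups were enrolled.

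A reader might go further and infer that the trial is underpowered. The documents do not support that. With unstated inputs the same design ranges from weak to strong: 20% to 97% for a sustained 0.05-point gap at score SD 0.15-0.20 and ρ 0-0.8, before any clustering.

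**What to change.** In Sample and Setting:

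1. Keep the PASS calculation as the record of how the size was set. Add its unit, error SD, correlation and pattern of means from the output, or say that they were not recorded.
2. Unless the output shows a unit that converts to the 0-1 score, state that the 100% does not apply to that score. In either case state that it ignores the randomised groups, and stop presenting it as the trial's power.
3. Add a short table for the existing 80+65 students in 5+5 groups: the difference in 0-1 points detectable with 80% power for the interaction (sustained and fading patterns) and for the single differences at T2, T3 and T4.
4. Label score SD, correlation, ICC and ε as assumptions and show ranges. For the interaction, show group effects that are constant and that vary over time. Do not use the observed effect. Say whether each figure belongs to the student-level ANOVA or to an analysis of the 10 groups.

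The cost is one rewritten paragraph and one small table, and a less favourable stated figure. Conduct and enrolment do not change.

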##### Developmental Process

Of the 300 eligible students, 145 agreed to participate. Block randomization was used for the random assignment of students to the experimental group (EG) and control group (CG). The unit of randomization was small groups (13-16 students/group), with all enrolled students assigned accordingly. Block randomization was performed using a random number generator, assigning 5 blocks to the experimental group (80 students) and 5 blocks to the control group (65 students).

Both groups (EG and CG) received BTI training in a brief format of 2.5 hours in groups of 13-16 students. The content included 1) general information and epidemiology of smoking, 2) passive smoking, 3) evidence of the effectiveness of smoking cessation interventions, and 4) the WHO's approach to smoking in Primary Care based on the 5 As and 5 Rs model to help patients quit smoking (World Health Organization, 2014). This model outlines the five main steps of the 5 As (Ask, Advise, Assess, Assist, and Arrange) for providing brief interventions in primary care and the 5 Rs (Relevance, Risks, Rewards, Roadblocks, and Repetition) to be addressed for a smoker who is not ready to quit at that moment.

The methodology included a phase of evaluating the students' learning using the Videotape Objective Structured Clinical Examination (VOSCE). Students were shown 3 recorded clinical scenarios (video-problems) with standardized patients in which a nursing professional performs a brief tobacco intervention (BTI) on a patient visiting a primary care clinic, following the 5 As and 5 Rs model. The videos depicted common errors in this type of intervention, and students were required to detect them using the validated BTI-St® assessment tool. The scenarios included the patient was not ready to quit smoking (scenarios 1 and 2) and was ready to quit (scenario 3).

The data collection protocol was similar in both the EG and CG, with five measurements conducted each time after viewing the 3 video-problems and assessing learning through the BTI-St®. At baseline, before BTI training (T0); followed by training in BTI in Primary Care (T1). Subsequently, in the experimental group, an expert instructor conducted a structured debriefing lasting 10-15 minutes for each clinical scenario, whereas no further intervention was provided in the control group. At the end of the first day, all participants viewed the videos and completed the tool again (T2). At three and nine months, students viewed the videos and measurements were taken at T3 and T4, respectively.

The debriefing used had the following characteristics: short ( $\leq 15$  minutes), educator present, educator with debriefing experience, the context was related to health management or decision-making, and the method used was the plus-delta tool, which asks participants to reflect on the simulation event and evaluate their performance by identifying strengths and areas for improvement.

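### Ten small groups were randomised but 145 students are analysed as independent, so the 5% error rate holds only if groups do not differ

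*Combined protocol and SAP*

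**What the plan says.** The Developmental Process section defines the randomised unit: "The unit of randomization was small groups (13-16 students/group), with all enrolled students assigned accordingly". It gives the allocation as "assigning 5 blocks to the experimental group (80 students) and 5 blocks to the control group (65 students". Both arms "received BTI training in a brief format of 2.5 hours in groups of 13-16 students", so students also shared a teaching session.

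The sentence just before the definition reads differently: "Block randomization was used for the random assignment of students to the experimental group (EG) and control group (CG". The procedure is called block randomisation throughout, and the word cluster does not appear.

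The Data Analysis section works at student level: "A two-factor repeated measures ANOVA was used to analyze the differences in within-subject and between-subject measures". For other comparisons between arms, "the t-Student test and Chi-Square test were used depending on the nature of the comparison variable". The only dependence it addresses is among a student's own repeated scores: "The assumptions of this test include the condition of sphericity", with a multivariate approach or the Greenhouse-Geisser correction if that condition fails. The sample size in Sample and Setting also counts individual subjects (65 per arm) and uses no ICC or design effect.

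**The concern.** When whole groups are allocated, the evidence about the arm effect comes from the variation between groups, and here there are five per arm. A student-level analysis takes its error term from variation between students. It uses 145 − 2 = 143 degrees of freedom for the arm comparison, where the randomisation supports 10 − 2 = 8. If students in one session score more alike than students in different sessions, the standard error is too small. Differences between a few sessions could then be read as an effect of debriefing. The Greenhouse-Geisser correction does not help, because it deals with correlation over time within a student and not with correlation between students.

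**Working it through.** **1. The plan's own figure.** Sample and Setting states 100% power for the arm-by-time interaction with 2 × 65 subjects, five measurements and an effect SD of 1. The calculation is a noncentral F with degrees of freedom 4ε and 512ε (4 = 1 × 4; 512 = 128 × 4) and λ = ε × 130 × 5 × 1² / [SD² × (1 − ρ)]. The SD and the correlation ρ between measurements are not given, so the figure cannot be reproduced exactly. With SD = 1, ρ = 0 and ε = 1, λ = 650 and power is 1.00. Taking ρ = 0, power stays at 99.5% or more up to an SD of about 2.8 (ε = 0.25) or 4.8 (ε = 1). The stated 100% is therefore possible, but it treats 130 students as independent and gives no protection against clustering.

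**2. Randomised units.** 80/5 = 16 and 65/5 = 13, the two ends of the stated size range. The mean is 145/10 = 14.5. The 5% critical value of t is 1.977 on 143 df and 2.306 on 8 df.

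**3. One time point.** The ICC is an assumption. Design effect = 1 + (14.5 − 1) × ICC, and effective N = 145 / design effect. The true variance of the arm difference, in units of the score variance, is (1 − ICC)(1/80 + 1/65) + ICC × 2/5. The student-level analysis uses 1/80 + 1/65 = 0.02788. For ICC 0.05: 0.95 × 0.02788 + 0.05 × 0.4 = 0.04649; 0.04649/0.02788 = 1.667; the square root is 1.29. The approximate error rate is 2 × [1 − Φ(1.96 / SE ratio)].

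| Assumed ICC | Design effect | Effective N | True SE / student-level SE | Actual error of a 5% student-level t test |
|---|---|---|---|---|
| 0.01 | 1.14 | 128 | 1.07 | 7% |
| 0.02 | 1.27 | 114 | 1.13 | 8% |
| 0.05 | 1.68 | 87 | 1.29 | 13% |
| 0.10 | 2.35 | 62 | 1.53 | 20% |

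Simulation agrees (7%, 9%, 13%, 20%).

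**4. ANOVA between-arm test.** This test averages five scores per student. Averaging reduces measurement noise but not a stable group effect, so the effective ICC is higher than in step 3. Assume a within-student correlation of 0.5 that includes the group share. The variance of a student's mean is then 0.5 + 0.5/5 = 0.6. At ICC 0.05 the ICC of that mean is 0.05/0.6 = 0.083, the design effect is 1 + 13.5 × 0.083 = 2.125, and the SE ratio is 1.46. The error rate is 2 × [1 − Φ(1.96/1.46)] = 18%. Null simulations (2,500 to 4,000 runs per setting, groups of 5 × 16 and 5 × 13) gave 10–11%, 18% and 26–29% at ICC 0.02, 0.05 and 0.10.

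**5. Arm-by-time test.** The result depends on when groups start to differ. Simulated error at a nominal 5%, by the assumed group share of variance:

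| Pattern of group effect | 0.02 | 0.05 | 0.10 |
|---|---|---|---|
| Stable from T0 | 4–5% | 4–5% | 4–5% |
| Starts at training and persists | 6–8% | 11–13% | 17–18% |
| Varies independently at each time | 19% | 40% | 64% |

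A share of 0.05 from training plus a further 0.05 from T2 gave 20–22%.

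**6. Controls.** With no clustering, the planned tests gave about 4–5%. A t test on the 10 group means (8 df) stayed at about 4–6% throughout.

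**The case against.** The strongest reply is that the size of the problem is unknown and that the key test may escape it. The documents give no ICC, and at an ICC of exactly zero nothing is inflated. The trial was sized on the arm-by-time interaction, where a stable group effect cancels. T1 is taken after training and before debriefing, so a persisting training-session effect also cancels in contrasts from T1 onward, the period that isolates debriefing. The simulated T1–T4 interaction test stayed at 4.8–5.5% under that pattern. These points stand. They limit the inflation of the interaction test to group differences that arise within the period tested. They do not rescue the plan: it tests all five times and a between-arm effect, and it offers no ground for assuming that groups respond alike to the session or to an instructor-led debriefing.

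Other points stand in part:

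- One sentence speaks of assigning students, and the protocol does not say how the small groups were formed. If students were placed in groups at random, a pre-existing group effect is less likely, but a shared-session effect remains. The explicit definition of the unit governs until the wording is reconciled.
- The t and chi-square tests may be meant only for baseline variables. The ANOVA has the same fault either way.
- The protocol does not say that group membership is in the dataset, and it describes personal codes for anonymity.

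**Conclusion.** The concern holds. The mismatch between the randomised unit and the analysed unit is explicit, and nothing else in the document repairs it. It must be corrected before the p-values can be taken at face value. The amount of inflation rests on assumed ICCs, a within-student correlation of 0.5 and an assumed timing of group effects. The between-arm test is the more exposed: even an ICC of 0.01 gave 7.7%. For the interaction test the plausible range runs from no inflation, if group effects are stable, to several times the nominal 5%, if groups vary over time. Confidence is high that the analysis is wrong for this design, and lower about the size of the error.

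**What to change.** - Describe the trial as cluster-randomised with 10 groups. Reconcile the two sentences on what was assigned, and say how the small groups were formed and whether allocation was restricted by academic year.
- Replace the student-level ANOVA with a linear mixed model for arm, time and their interaction. Include random effects for small group, for group differences in change over time, and for student, with Satterthwaite or Kenward-Roger degrees of freedom.
- Alternatively, compare the 10 group means with a t test on 8 df, stating the baseline used: change from T1 isolates debriefing and change from T0 does not. A permutation test is also possible. With unrestricted allocation there are 252 arrangements and the smallest two-sided p is 2/252 = 0.008. Restriction by year would leave fewer arrangements and a larger minimum.
- Apply the same principle to any t or chi-square test of an outcome, and report the ICC.

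The cost is revised analysis text and a re-run, with no new data provided that small-group membership can be linked to the personal codes. Intervals become wider. At one time point the half-width grows by the SE ratio times 2.306/1.977, which is about 1.31, 1.51 and 1.78 times at ICC 0.02, 0.05 and 0.10.

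### Groups appear to be assigned before the shared training and T0/T1 with no concealment described, and the five-time interaction test cannot separate a training difference from a debriefing effect

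*Combined protocol and SAP*

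**What the plan says.** All quotes are from the Developmental Process section of the protocol.

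- Unit of assignment: "The unit of randomization was small groups (13-16 students/group), with all enrolled students assigned accordingly".
- Assignment: "Block randomization was performed using a random number generator, assigning 5 blocks to the experimental group (80 students) and 5 blocks to the control group". The control arm has 65 students.
- Common training, described next and by arm label: "Both groups (EG and CG) received BTI training in a brief format of 2.5 hours in groups of 13-16 students".
- First two measurements: "At baseline, before BTI training (T0); followed by training in BTI in Primary Care (T1".
- Start of the contrast, experimental arm: "Subsequently, in the experimental group, an expert instructor conducted a structured debriefing lasting 10-15 minutes for each clinical scenario".
- Control arm at the same point: "whereas no further intervention was provided in the control group".
- Equality of the arms: "The data collection protocol was similar in both the EG and CG, with five measurements conducted each time". This concerns data collection and says nothing about how the training was delivered.

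The Sample and Setting section sizes the trial on the group-by-time interaction over five measurements. The Data Analysis section plans a two-factor repeated measures ANOVA and names no contrast that starts at T1. Nowhere do the documents say when the sequence was drawn, who held it, who knew a group's arm during training, or who taught which groups.

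**The concern.** Up to T1 the two arms are meant to receive the same thing, so nobody needs to know a group's arm until then. As the text reads, the arm is already fixed when the training is taught, and the randomized groups match the training groups in size. Each session then belongs to one arm. Anything that differs between sessions becomes a difference between arms: an instructor's emphasis if the arm is known, students' effort if they know it, or simply one session going better than another. The same three videos are scored at every measurement, so emphasis on their errors in training can move the score directly.

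The analysis offers no protection as planned. The trial's aim is the effect of debriefing, but the five-time interaction also responds to a change between T0 and T1, before any debriefing. A significant result could not be assigned to debriefing without a further contrast.

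**Working it through.** **1. Group sizes.** 80/5 = 16 and 65/5 = 13. These are the two ends of the stated range of 13 to 16, so on the stated figures every experimental group has 16 students and every control group 13. This fits the reading that randomized groups and training groups are the same. If so, the shared training was given in groups of different size in the two arms; the documents give no sign of whether that matters.

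**2. The plan's own figure.** The power stated is 100% for the interaction with N = 130, T = 5, effect SD 1 and a 5% level. Noncentrality is λ = N·T·σ_AB²/[σ²(1−ρ)]. Error SD and correlation are not given; with σ = 1 and ρ = 0 assumed, λ = 130 × 5 × 1 = 650 and power is 100%, even at the lowest possible Greenhouse-Geisser ε of 0.25. At σ = 3 the worst case is still 98.8%. The figure reproduces. It concerns the five-time interaction, the test examined below.

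**3. That test when only the training differs.** Assumptions: no debriefing effect; an arm gap of d SD absent at T0 and present at T1 to T4; equal correlation ρ between measurements; 80 and 65 independent students. The gap pattern is (0, 1, 1, 1, 1), with mean 0.8 and sum of squared deviations 0.64 + 4 × 0.04 = 0.80. Hence

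λ = [80 × 65/145] · d² · 0.80/(1−ρ) = 35.86 · d² · 0.80/(1−ρ),

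referred to F with 4 and 4 × 143 = 572 degrees of freedom. Simulation of the Greenhouse-Geisser test (3,000 trials per setting) agrees.

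| ρ | λ at d = 0.2 | Formula, d = 0.2 | Simulated, d = 0 | d = 0.2 | d = 0.3 | d = 0.5 |
|---|---|---|---|---|---|---|
| 0.3 | 1.64 | 14.6% | 5.2% | 14.5% | 27.7% | 72.0% |
| 0.5 | 2.30 | 19.1% | 4.9% | 18.7% | 39.8% | 86.6% |
| 0.7 | 3.83 | 30.4% | 4.1% | 30.3% | 62.2% | 98.6% |

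**4. Tests that start at T1, same simulated data.** From T1 on the gap pattern is flat, so λ = 0. The T1-to-T2 change and the T1-to-T4 interaction reject in 4.4% to 5.8% of trials throughout.

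**5. Ordinary variation between sessions.** Suppose no arm-related teaching at all, but sessions differ with SD 0.2 or 0.3 from T1 on (assumed). With five sessions per arm the arm gap has SD 0.2 × √(1/5 + 1/5) = 0.13, or 0.3 × √(2/5) = 0.19. The five-time interaction then rejects in about 10% and 17% of trials at ρ = 0.5, and in about 9% to 23% over ρ = 0.3 to 0.7. The T1-to-T4 interaction stays near 5%.

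**6. Limits of starting at T1.** If a 0.5 SD gap halves by T2 and is gone by T3 (ρ = 0.5), the T1-to-T2 change rejects in 31% of trials and the T1-to-T4 interaction in 84%, with no debriefing effect. Adjusting T2 to T4 for T1 as a covariate also differs from taking change. It removes only the regression slope's share of a lasting gap, and under equal correlation that slope is about ρ. At d = 0.2 and ρ = 0.5, 0.2 × (1 − 0.5) = 0.1 SD remains.

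**The case against.** A reader might infer that the allocation was open, that the training was taught unequally, and that the planned test will credit this to debriefing. The documents do not support that. They are silent on concealment, which is not a statement that there was none. That assignment came before T0 rests on paragraph order. Both arms have the same 2.5-hour format and content list, and no evidence shows unequal delivery. A gap could favour either arm, so it could also mask a debriefing effect. Even at 0.2 SD and ρ = 0.5 the test does not reject in about four of five trials. All of this stands, and it limits the point to a risk.

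Two further objections also stand. T1 is measured in both arms before debriefing, so a gap would be visible and a contrast from T1 could separate a lasting one; the plan simply does not specify that contrast. And concealment alone would not remove ordinary variation between sessions, so it is only part of the remedy.

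What the objections do not remove is the structure: nothing before T1 needs the allocation, no safeguard is described, and the planned interaction includes a step that debriefing cannot have caused.

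**Conclusion.** The concern holds as an avoidable design risk, not as demonstrated bias. Under no debriefing effect, a lasting training gap of 0.2 SD raises rejection by the five-time interaction from about 5% to about 14% to 30% for correlations of 0.3 to 0.7. Gap size and correlation are assumptions with no anchor in the documents, the direction is unknown, and these figures treat students as independent. Variation between sessions alone gives about 9% to 23% at an assumed session SD of 0.2 to 0.3. Two readings are inferred and should be confirmed: that arms were fixed before T0, and that each training session belonged to a single arm.

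**What to change.** **Procedure, for sessions still to be held.** Keep the random assignment of groups, but have it held outside the teaching team, for example in one sealed envelope per group, and opened only after that group's T1 forms are collected. Use the same timetable in both arms so that the schedule does not reveal the arm.

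**Analysis.** Start the debriefing contrast at T1, preferably as change from T1 to T2, T3 and T4. T2 to T4 adjusted for T1 is an alternative, but it leaves part of a lasting gap, as shown above. Report the arm difference at T1.

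**If the sessions are complete**, as the past tense suggests, state when randomization took place, who knew each group's arm during training and who taught each group. Use the contrast from T1, and acknowledge that it does not remove a gap that fades after T1.

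**Cost.** Ten envelopes, a short protocol paragraph and a debriefer on call for every session. Control sessions would hold an idle slot of 3 × 10 to 3 × 15 = 30 to 45 minutes. With a fixed 5/5 split the last assignments become partly predictable, so concealment would be weaker for the later groups. The change of contrast needs no new data.
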